NON-INTERVENTIONAL STUDY PROTOCOL

Study information

Title	Cost comparison between apixaban and low molecular weight heparin (LMWH) among venous thromboembolism (VTE) cancer patients
Protocol number	B0661183
Protocol version identifier	2.0
Date	29 July 2022
Research question and objectives	
To evaluate the costs and healthcare resource utilization (HCRU) associated with treating VTE cancer patients with apixaban compared to LMWH
 
To compare costs and HCRU associated with recurrent VTE, major bleeding, and clinically relevant non-major (CRNM) bleeding among VTE cancer patients treated with apixaban vs LMWH

Authors	
PPD
 
IQVIA
 
PPD
 
[name]

090177e19b7d94e0\Approved\Approved On: 29-Aug-2023 01:40 (GMT)

2. LIST OF ABBREVIATIONS

Abbreviation	Definition
AE	adverse event
ACE	Angiotensin-converting enzyme
AIDS	acquired immune deficiency syndrome
APS	antiphospholipid syndrome
ARB	Angiotensin receptor blockers
ASH	American Society of Hematology
BMS	Bristol Myers Squibb
CCI	Charlson comorbidity index
COPD	chronic obstructive pulmonary disease
CRNM	clinically relevant non-major bleeding
DCTs	data collection tools
DVT	deep vein thrombosis
ER	emergency room
ESA	Erythropoiesis stimulating agents
GI	gastrointestinal
GLM	generalized linear models
HCPCS	healthcare common procedure coding system
HCRU	healthcare resource utilization
HIPAA	health insurance portability and accountability act
HMO	health maintenance organization

PFIZER CONFIDENTIAL

CT24-WI-GL02-RF02 4.0 Non-Interventional Study Protocol Template For Secondary Data Collection Study 01-Jun-2022

Page 4 of 35

090177e19b7d94e0\Approved\Approved On: 29-Aug-2023 01:40 (GMT)

Apixaban

B0661183 NON-INTERVENTIONAL STUDY PROTOCOL

Protocol Version: 2.0 29 July 2022

ICD-10-CM	international classification of diseases, tenth revision, clinical modification
ICH	intracranial hemorrhage
ID	identifier
IEC	independent ethics committee
IPTW	inverse probability of treatment weighting
IQR	Interquartile range
IRB	institutional review board
LMWH	low molecular weight heparin
LOS	Length of stay
NDC	National Drug Codes
NSAID	Nonsteroidal anti-inflammatory drugs
OAC	oral anticoagulant
PAC	parenteral anticoagulant
PCP	primary care provider
PE	pulmonary embolism
PPO	preferred provider organization
SAS	statistical analysis system
SCHIP	State Children's Health Insurance Program
SD	standard deviation
SERM	Selective estrogen receptor modulators
SMD	standardized mean difference
US	United States

PFIZER CONFIDENTIAL

CT24-WI-GL02-RF02 4.0 Non-Interventional Study Protocol Template For Secondary Data Collection Study 01-Jun-2022

Page 5 of 35

090177e19b7d94e0\Approved\Approved On: 29-Aug-2023 01:40 (GMT)

Apixaban
B0661183 NON-INTERVENTIONAL STUDY PROTOCOL
Protocol Version: 2.0 29 July 2022

USD	United States dollars
VTE	venous thromboembolism

090177e19b7d94e0\Approved\Approved On: 29-Aug-2023 01:40 (GMT)

4. ABSTRACT

Title

Cost comparison between apixaban and low molecular weight heparin (LMWH) among venous thromboembolism (VTE) cancer patients

Version: 2.0

Date: 29 July 2022

Primary author:

PPD

Pfizer, Inc.

Rationale and background

Venous thromboembolism (VTE), comprising deep vein thrombosis (DVT) and pulmonary embolism (PE), is a common complication in patients with cancer. The risk of developing VTE in these patients is four to seven times higher compared to patients without cancer, with a reported incidence of up to 15% per year.^{1,2} American Society of Hematology (ASH) guidelines recommend direct-acting oral anticoagulants (OAC) or low molecular weight heparin (LMWH) in ambulatory patients with cancer at high risk for VTE or for initial treatment of VTE.⁴

The risk of recurrent VTE, despite anticoagulant therapy, and bleeding complications is higher among patients with cancer compared to those without cancer.⁵ Apixaban, an oral factor Xa inhibitor has been previously shown to be efficacious in treating cancer-associated VTE without increased risk of major bleeding.⁷ There is a lack of evidence comparing the direct medical cost of using LMWH with direct-acting OAC's such as apixaban which has been previously demonstrated to decrease the risk of recurrent VTE and major bleeding in cancer patients with VTE.^{8,9} Therefore, this study will evaluate the costs and healthcare resource utilization (HCRU) associated with treating VTE cancer patients with apixaban compared to LMWH.

Research question and objectives

The purpose of this study is to evaluate the costs and HCRU associated with treating VTE cancer patients with apixaban compared to LMWH (dalteparin or enoxaparin).

The objectives of the study are as follows:

Primary objectives:

- To compare all-cause healthcare costs among VTE patients with cancer treated with apixaban vs LMWH

PFIZER CONFIDENTIAL

CT24-WI-GL02-RF02 4.0 Non-Interventional Study Protocol Template For Secondary Data Collection Study 01-Jun-2022

Page 8 of 35

090177e19b7d94e0\Approved\Approved On: 29-Aug-2023 01:40 (GMT)

Apixaban**B0661183 NON-INTERVENTIONAL STUDY PROTOCOL**Protocol Version: 2.0 29 July 2022

- To compare costs associated with recurrent VTE, major bleeding, and clinically relevant non-major (CRNM) bleeding among VTE patients with cancer treated with apixaban vs LMWH

Secondary objectives:

- To compare all-cause HCRU among VTE patients with cancer treated with apixaban vs LMWH
- To compare HCRU associated with recurrent VTE, major bleeding, and CRNM bleeding among VTE patients with cancer treated with apixaban vs LMWH

Study design

A retrospective database analysis will be conducted using IQVIA's PharMetrics® Plus database among newly diagnosed VTE patients with active cancer who received apixaban or a LMWH on or within 30 days following the VTE diagnosis. The analysis will be conducted using data from 01 January 2016 through 31 December 2021 (i.e., the *study period*), including a 12-month pre-index period and 1-month post-index period and patients will be followed through the earliest of the following: health plan disenrollment, index therapy discontinuation, switch to another anticoagulant or end of study period.

Population

Adult patients with evidence of cancer and newly diagnosed VTE, followed by a claim of apixaban or LMWH will be identified. The date of the first apixaban or LMWH prescription will be termed as the index date and two cohorts will be identified based on this index prescription. Patient will be continuously enrolled during the 12-month pre-index period and with a variable post-index period. Other exclusion criteria will also be applied such as patients with evidence of atrial fibrillation, mechanical heart valve, inferior vena cava filter, antiphospholipid syndrome, pregnancy and with any data quality issues.

Variables*Exposures and explanatory variables in the pre-index period or on index date:*

- Demographic characteristics
- Clinical characteristics
- Baseline HCRU and costs

Outcomes

- All-cause HCRU and costs
- Recurrent VTE related HCRU and costs
- Major bleeding related HCRU and costs
- CRNM bleeding related HCRU and costs

Data sources

IQVIA's PharMetrics® Plus database comprises adjudicated claims for more than 190 million unique enrollees across the United States (US). Enrollees with both medical and pharmacy coverage in 2020 represented 40 million lives. PharMetrics Plus has diverse representation of

PFIZER CONFIDENTIAL

CT24-WI-GL02-RF02 4.0 Non-Interventional Study Protocol Template For Secondary Data Collection Study 01-Jun-2022

Page 9 of 35

090177e19b7d94e0\Approved\Approved On: 29-Aug-2023 01:40 (GMT)

Apixaban

B0661183 NON-INTERVENTIONAL STUDY PROTOCOL

Protocol Version: 2.0 29 July 2022

geography, employers, payers, providers and therapy areas. Patients in each zip code and every Metropolitan Statistical Area of the US are included, with coverage of data from 90% of US hospitals, 80% of all US doctors, and representation from 85% of the Fortune 100 companies. In addition to standard fields such as inpatient and outpatient diagnosis and procedures, retail and mail-order prescription records, PharMetrics Plus has detailed information on the pharmacy and medical benefit (copayment, deductible), the inpatient stay (admission type and source, discharge status) and provider details (specialty, provider identifier [ID]). Payment amounts include the negotiated rate between the plan and providers (allowed) and the actual amount paid by health plans to the provider for all services rendered. Charge amount is also available for a subset of claims. Other data elements include dates of service, demographic variables (age, gender, and geographic region), product type (e.g., health maintenance organization [HMO], preferred provider organization [PPO]), payer type (e.g., commercial, self-insured), and start and stop dates of health-plan enrollment.

Study size

An earlier feasibility study estimated that there were 4,972 VTE patients with cancer with evidence of apixaban in PharMetrics® Plus.

A minimum sample of 1,867 patients in each cohort is required to achieve 80% power at a 5% level of significance (two-sided) using recurrent VTE event rates from Agnelli et al.⁷ of 5.6% in apixaban cohort and 7.9% in dalteparin cohort. Using recurrent VTE rates 4.362% in apixaban cohort and 6.483% in LMWH cohort from Cohen et al.,⁸ we require a minimum sample of 1,788 patients in each cohort to achieve 80% power. Based on the sample size calculations, for the current study we need a minimum sample in the range of 1,788-1,867 patients in each cohort.

Data analysis

Descriptive statistics will be produced for all relevant study measures, for the 2 therapy cohorts. Stabilized inverse probability treatment weighting (IPTW) will be used to balance patient characteristics between apixaban and LMWH cohorts. Post-IPTW, comparisons will be conducted using weighted chi-square tests for categorical variables and weighted t-tests (mean) for continuous variables. Comparisons between independent samples (e.g., among patients with ≥ 1 hospitalization) and pre-IPTW samples will be conducted using the parametric t-test (mean) and non-parametric Wilcoxon rank-sum test (median) for continuous variables. A p value of ≤ 0.05 will be considered significant.

Up to 4 regression models will be developed and these may include weighted generalized linear models (GLM) with log transformation and gamma distribution to estimate adjusted (all-cause) cost ratio between the two cohorts or a negative binomial distribution may be developed to estimate adjusted visits such as physician office visits, emergency room visits or other HCRU.

Milestones

Protocol and table shells: 12 August 2022

Start of data analysis: 15 August 2022

PFIZER CONFIDENTIAL

CT24-WI-GL02-RF02 4.0 Non-Interventional Study Protocol Template For Secondary Data Collection Study 01-Jun-2022

Page 10 of 35

090177e19b7d94e0\Approved\Approved On: 29-Aug-2023 01:40 (GMT)

Apixaban

B0661183 NON-INTERVENTIONAL STUDY PROTOCOL

Protocol Version: 2.0 29 July 2022

Final results: 21 October 2022

Final study reports and presentation: 18 November 2022

090177e19b7d94e0\Approved\Approved On: 29-Aug-2023 01:40 (GMT)

PFIZER CONFIDENTIAL

CT24-WI-GL02-RF02 4.0 Non-Interventional Study Protocol Template For Secondary Data Collection Study 01-Jun-2022

Page 11 of 35

Apixaban
B0661183 NON-INTERVENTIONAL STUDY PROTOCOL
Protocol Version: 2.0 29 July 2022

5. AMENDMENTS AND UPDATES

Amendment number	Date	Protocol section(s) changed	Summary of amendment(s)	Reason
None				

090177e19b7d94e0\Approved\Approved On: 29-Aug-2023 01:40 (GMT)

6. MILESTONES

Milestone	Planned date
Protocol approval	12 August 2022 (estimated)
Start of analysis	15 August 2022 (estimated)
Analysis completion	21 October 2022 (estimated)
Final study report	18 November 2022 (estimated)

090177e19b7d94e0\Approved\Approved On: 29-Aug-2023 01:40 (GMT)

Apixaban

B0661183 NON-INTERVENTIONAL STUDY PROTOCOL

Protocol Version: 2.0 29 July 2022

7. RATIONALE AND BACKGROUND

Venous thromboembolism (VTE), comprising deep vein thrombosis (DVT) and pulmonary embolism (PE), is a common complication in patients with cancer. The risk of developing VTE in these patients is four to seven times higher compared to patients without cancer, with a reported incidence of up to 15% per year.^{1,2} Several cancer-associated risk factors for VTE have been identified, including patient-, treatment-, and tumor-related factors. Currently, patients with cancer often undergo imaging for tumor staging and evaluation of treatment response, which further increases the underlying possibility of VTE detection.³ When VTE is diagnosed, anticoagulant therapy is indicated in most cases. 2021 American Society of Hematology (ASH) guidelines recommend direct-acting oral anticoagulants (OAC) or low molecular weight heparin (LMWH) in ambulatory patients with cancer at high risk for VTE or for initial treatment of VTE.⁴ However, the management of VTE remains challenging in this patient population. The risk of recurrent VTE, despite anticoagulant therapy, and bleeding complications is higher among patients with cancer compared to those without cancer.⁵ Recurrent VTE among patients with cancer is associated with significant healthcare resource use and, notably, hospitalizations.⁶

Apixaban, an oral factor Xa inhibitor has been previously shown to be efficacious in treating cancer-associated VTE without increased risk of major bleeding.⁷ A study Cohen A. et al.⁸ compared LMWH to apixaban for the treatment of VTE associated with cancer, however this study primarily focused on the effectiveness and safety profile of these treatments. Another study by Hlavacek et al.⁹ compared healthcare costs of major bleeding and CRNM bleeding but this study was conducted only among VTE patients. Apixaban has been demonstrated to decrease the risk of recurrent VTE and major bleeding in cancer patients with VTE, however, there is a lack of evidence comparing the direct medical cost of using LMWH with direct-acting OAC's among such patients. Therefore, this study will evaluate the costs and healthcare resource utilization (HCRU) associated with treating VTE cancer patients with apixaban compared to LMWH.

090177e19b7d94e0\Approved\Approved On: 29-Aug-2023 01:40 (GMT)

PFIZER CONFIDENTIAL

CT24-WI-GL02-RF02 4.0 Non-Interventional Study Protocol Template For Secondary Data Collection Study 01-Jun-2022

Page 14 of 35

Apixaban

B0661183 NON-INTERVENTIONAL STUDY PROTOCOL

Protocol Version: 2.0 29 July 2022

8. RESEARCH QUESTION AND OBJECTIVES

The purpose of this study is to evaluate the costs and HCRU associated with treating VTE cancer patients with apixaban compared to LMWH (dalteparin, enoxaparin, or tinzaparin).

The objectives of the study are as follows:

Primary objectives:

- To compare all-cause healthcare costs among VTE patients with cancer treated with apixaban vs LMWH
- To compare costs associated with recurrent VTE, major bleeding, and clinically relevant non-major (CRNM) bleeding among VTE patients with cancer treated with apixaban vs LMWH

Secondary objectives:

- To compare all-cause HCRU among VTE patients with cancer treated with apixaban vs LMWH
- To compare HCRU associated with recurrent VTE, major bleeding, and CRNM bleeding among VTE patients with cancer treated with apixaban vs LMWH

090177e19b7d94e0\Approved\Approved On: 29-Aug-2023 01:40 (GMT)

PFIZER CONFIDENTIAL

CT24-WI-GL02-RF02 4.0 Non-Interventional Study Protocol Template For Secondary Data Collection Study 01-Jun-2022

Page 15 of 35

9. RESEARCH METHODS

[figure not shown]
A retrospective database analysis will be conducted among newly diagnosed VTE patients with active cancer who received apixaban or a LMWH on or within 30 days following the VTE diagnosis. IQVIA’s PharMetrics® Plus will be used for this analysis. See Annex 2.

9.1. Study period and study design

The analysis will be conducted using data from 01 January 2016 through 31 December 2021 or the latest available data at the time of extraction (i.e., the *study period*). Patients will be identified during a *selection window* of 01 January 2017 to 31 October 2021. The date of the first apixaban or LMWH prescription on or within the 30 days following a VTE diagnosis will be termed as the index date. Patients will be required to have continuous enrollment with medical and pharmacy benefits for 12-months prior to the index date to assess study eligibility criteria and to measure baseline characteristics (*the baseline or pre-index period*). Patients will also be required to have continuous enrollment with medical and pharmacy benefits for at least one month (30 days) starting on and following the index date (the follow-up or post-index period) and will be followed through the earliest of the following: health plan disenrollment, index therapy discontinuation, switch to another anticoagulant (includes switch to the other study medication or unfractionated heparin, fondaparinux, warfarin, rivaroxaban, dabigatran, or edoxaban), or end of study period (31 December 2021).

Note: Patients in the LMWH cohort will NOT be considered to have discontinued or switched if they change to an LMWH other than the index LMWH (dalteparin, enoxaparin, or tinzaparin).

Figure 1. Study Period

9.1.1. Inclusion criteria

Patients must meet all of the following inclusion criteria to be eligible for inclusion in the study:

090177e19b7d94e0\Approved\Approved On: 29-Aug-2023 01:40 (GMT)

Apixaban

B0661183 NON-INTERVENTIONAL STUDY PROTOCOL

Protocol Version: 2.0 29 July 2022

1. Patients with ≥ 1 diagnosis code for VTE (inpatient [primary or secondary discharge diagnosis] or any position on an outpatient non-ancillary medical claim) between January 1, 2017 and October 31, 2021 (selection window).
 - Note: Qualifying outpatient encounters followed by qualifying inpatient encounters within 7 days will be considered an inpatient VTE event, unless LMWH or apixaban was initiated between encounters, in which case it will be classified as an outpatient VTE event
 - First date of claim with a VTE diagnosis code will be termed the ‘index VTE encounter’

2. Evidence of having active cancer, defined as ≥ 2 medical claims with a cancer diagnosis (excluding nonmelanoma skin cancer) on different days during the 6 months before or within 30-days after the index VTE event

OR

≥ 1 medical claim for a cancer diagnosis AND ≥ 1 claim for cancer treatment (eg: chemotherapy, radiation, immunotherapy, hormone therapy or cancer related surgery using national drug codes (NDC), international classification of diseases, tenth revision, clinical modification [ICD-10-CM] procedure codes or healthcare common procedure coding system [HCPCS] codes) during 6 months before or within 30 days after the index VTE encounter

3. ≥ 1 claim of apixaban or LMWH (dalteparin orenoxaparin) on or within 30 days following the index VTE encounter.
 - a. The date of the first apixaban or LMWH prescription fill will be designated as the index date
4. ≥ 12 months of continuous enrollment prior to the index date (pre-index)
5. ≥ 1 months of continuous enrollment including and following the index date (post-index)
 - a. Note: Each patient will have a variable follow-up period with a minimum of 1-month follow-up. Patients will be followed from the day after the index date through the earliest of the following: health plan disenrollment, index therapy discontinuation, switch to another anticoagulant, or study end (December 31, 2021).
 - b. Discontinuation will be defined as occurrence of a ≥ 30 day gap from the run-out of days’ supply of the index LMWH or apixaban prescription. The date of the discontinuation will be defined as the last day of the days’ supply of the last filled prescription.
 - c. Switching will be defined as a prescription for an anticoagulant other than the index apixaban/LMWH prescription (unfractionated heparin, fondaparinux, other OAC, or LMWH for patients indexed on apixaban; unfractionated

PFIZER CONFIDENTIAL

CT24-WI-GL02-RF02 4.0 Non-Interventional Study Protocol Template For Secondary Data Collection Study 01-Jun-2022

Page 17 of 35

090177e19b7d94e0\Approved\Approved On: 29-Aug-2023 01:40 (GMT)

Apixaban**B0661183 NON-INTERVENTIONAL STUDY PROTOCOL**

Protocol Version: 2.0 29 July 2022

heparin, fondaparinux, or OAC (including apixaban) for patients indexed on LMWH) within 30 days following discontinuation of the index medication.

Note: Patients indexed on LMWH cohort will NOT be considered to have discontinued or switched if they change to an LMWH other than the index LMWH (dalteparin, enoxaparin, or tinzaparin)

6. ≥ 18 years of age at index

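### Active cancer can be established wholly by claims dated after the index fill, so cohort entry can depend on follow-up claims that also count in the cost outcome

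*Combined protocol and SAP*

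**What the plan says.** Criterion 2 in Section 9.1.1 offers two routes to active cancer. The first is at least two cancer diagnosis claims "on different days during the 6 months before or within 30-days after the index VTE event". The second is at least one diagnosis claim and at least one cancer treatment claim "during 6 months before or within 30 days after the index VTE encounter". Both windows are tied to the VTE, not to the first fill.

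Criterion 3 requires a study-drug claim "on or within 30 days following the index VTE encounter" and sets time zero: "The date of the first apixaban or LMWH prescription fill will be designated as the index date". Criterion 5 starts the outcome clock: "Patients will be followed from the day after the index date through the earliest of the following" (disenrollment, discontinuation, switch, study end). Section 9.1 requires enrollment of "at least one month (30 days) starting on and following the index date".

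No criterion asks for a cancer claim on or before the index date. Section 9.3.1 measures cancer site, type and treatment over the same window as criterion 2, while other clinical characteristics are measured pre-index. Section 9.7 plans no analysis restricted to cancer recorded before the fill, and the limitations in Section 9.9 do not mention the issue.

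**The concern.** The study compares patients who start one of two drugs, so membership of the cohort should be settled by what is on record at the start. Here it can be settled by what happens afterwards. A patient with no cancer claim at the fill enters if the claims arrive by day 30 after the VTE, and is left out if they do not.

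The deciding claims (work-up, diagnosis, surgery, chemotherapy) are also part of total all-cause cost, a primary outcome (Sections 8 and 9.3.2). Entry is then partly selected on the outcome. A bleed that prompts a work-up and a cancer code could both admit a patient and count among the bleeding costs of Section 9.3.3.

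Weighting is not a dependable remedy. Baseline comorbidities and costs are pre-index and do not show what admitted a late qualifier. The cancer covariates run to day 30 after the VTE, so they can look balanced without showing whether cancer was recorded before or after the drug was dispensed.

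**Working it through.** The plan gives no figure on this point. Its one computed figure, 1,788 to 1,867 patients per cohort (Section 9.5), reproduces with the pooled two-proportion formula and is not in dispute. The check is date arithmetic.

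**Inputs (Sections 9.1 and 9.1.1).** Let the VTE be day 0. The cancer window closes on day 30. The index fill is on day d, with 0 ≤ d ≤ 30. Follow-up starts on day d + 1.

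**Step 1: follow-up that can decide entry.** Days d + 1 to 30 lie in both the cancer window and the post-index period, which is 30 − d days.

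| Fill on day d | Post-index days on which a cancer claim still counts |
|---|---|
| 0 | 30 |
| 3 | 27 |
| 7 | 23 |
| 14 | 16 |
| 21 | 9 |
| 30 | 0 |

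For every fill before day 30, part of the window is post-index. These are upper limits, because follow-up can end earlier through discontinuation or switch.

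**Step 2: who is admitted.** Take three patients who each have a qualifying pair of claims by day 30.

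| Timing of the qualifying claims | Current rule | Both claims by the index date | One diagnosis claim by the index date, confirming claim to day 30 |
|---|---|---|---|
| Both before the fill | in | in | in |
| Diagnosis before, confirming claim after | in | out | in |
| Both after the fill | in | out | out |

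Only the third patient had no qualifying cancer claim when the drug was dispensed. A cut-off on both claims would also remove the second, whose cancer was already recorded.

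**Step 3: how the admitting claims enter the outcome.** Section 9.3.2 divides each patient's cost by follow-up days and multiplies by 30. If the admitting claims cost C and follow-up is F days, they add 30C/F to the monthly cost: C when F = 30, and C/2 when F = 60. Early costs weigh most when follow-up is short.

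**Step 4: when this biases the comparison.** Let p be the share of patients who qualify only on post-index claims, and k their monthly cost relative to the other patients in the same cohort. Use subscripts A for apixaban and L for LMWH. If the other patients have equal mean costs in the two cohorts, the crude LMWH/apixaban ratio is

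(1 − p_L + p_L·k_L) / (1 − p_A + p_A·k_A).

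This equals 1 when p and k are the same in both cohorts. It moves below or above 1 according to which cohort has the larger p(k − 1). The documents give neither p nor k.

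**Step 5: survival.** Required enrollment covers days d to d + 29. The cancer window runs beyond that by 30 − (d + 29) = 1 − d days, which is one day for a day-0 fill and none for later fills.

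**The case against.** The strongest reply is that the window is a deliberate choice, stated openly and applied equally to both cohorts. Cancer is often coded around a VTE, and a claim date is not the date on which a clinician knew. A rule common to both cohorts biases the ratio only if its effects differ between them. This stands as a limit on what can be claimed. It does not show that the effects are equal, and the plan would not reveal it if they were not.

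A reader might infer several stronger things that the documents do not support:

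- **That Section 9.1 contradicts criterion 2.** It calls for enrollment "for 12-months prior to the index date to assess study eligibility criteria and to measure baseline characteristics". That gives the purpose of the enrollment requirement. It does not say that all eligibility is settled there: criterion 5 and exclusions 5 to 7 also use post-index data.
- **That these patients had no known cancer, or cancer-free, low-cost baselines.** Only the absence of a claim is shown. Criterion 2 looks back 6 months from the VTE, while the baseline is 12 months, so older cancer claims may exist. No baseline cost is given for this group.
- **That the qualifying claims usually follow the fill.** Time from VTE to fill is a planned descriptive variable without a value.
- **That the rule adds immortal time.** Step 5 shows that it adds at most one day to the enrollment already required.
- **That the bias can be sized.** With assumed shares of 5–15% on apixaban and 2–3% on LMWH, and k of 1.5–2, the formula gives 1.01/1.025 = 0.985 to 1.02/1.15 = 0.887. Exchanging the shares gives 1.015 to 1.127. All inputs are assumptions, and the formula ignores weighting and regression adjustment, so this is not an estimate.

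The bleed-then-diagnosis sequence likewise shows what the rule permits, not how often it occurs.

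**Conclusion.** The point holds as a matter of design. Active cancer can rest entirely on claims after time zero. Up to 30 − d days of follow-up can decide entry, and the deciding claims are also outcome costs. This follows from Section 9.1.1 without further assumption.

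Bias in the cost comparison is conditional: patients who qualify only on post-index claims must differ between cohorts in share or relative cost. Size and direction cannot be computed from the documents, and the protocol describes no analysis that would reveal or bound them. The stated sample size is unaffected. This is a route to bias that should be closed or measured, not evidence that the result will be wrong.

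**What to change.** Define a restricted version of criterion 2. At least one cancer diagnosis claim must fall in the period from 6 months before the index VTE through the index date. The confirming claim (second diagnosis or treatment) may fall up to day 30 after the VTE, as now.

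Run the analysis under both the restricted and the current definitions. At minimum, prespecify the restricted one as a sensitivity analysis.

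In the attrition table that Section 9.1.2 already foresees, report by cohort how many patients qualify only on post-index claims, meaning that their first cancer diagnosis claim in the window is dated after the index date.

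The restriction does not end all reliance on post-index data, because the confirming claim may still follow the fill. It does ensure that a cancer diagnosis was on record when the drug was dispensed.

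**Cost:** one date condition in the cohort program, one protocol sentence and one extra analysis run. Some patients whose cancer was first coded after the fill leave the restricted analysis. The feasibility count of 4,972 apixaban patients against 1,788 to 1,867 needed suggests room in that cohort, but other criteria will reduce it and no LMWH count is given.
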